10.1.4.3 Accessibility Barriers

- Reach

Proportion of patients sent the decision/total number of patients seen in clinic after cross-over to intervention arm. This will be calculated using the numbers of patients who were offered the decision aid and who were sent the decision aid, and either billing records or clinic schedules (site preference as best way to determine number of patients seen during time period that would have been eligible to receive the decision aid).

- Reason for decline of decision aid
- Accessibility

We use adaptations of the four principles of accessibility outlined by in the Web Content Accessibility Guidelines (perceivable, operable, understandable, and robust), combined with other key concepts relevant to our study.⁸¹ We will collect data on acceptability of email delivery, how patients who accepted the decision aid used it, and the acceptability of the decision aid itself via survey. We will record the number of times the site was accessed by each patient via the Health Dialog company.

- Health Literacy

We use the Brief Health Literacy Screen (BHLS) to evaluate health literacy in clinical practice.⁸² The BHLS is a validated measure that has been evaluated in both the research and clinical setting. It consists of three items and takes approximately 1 minute to complete.

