Here, y_{ijk} denotes the response of the i^{th} level-1 unit (patient) of the j^{th} level-2 unit (surgeon) of the k^{th} level-3 unit (clinic). The variable x_{ijk} ($=0, 1$) denotes the intervention status of patient i from surgeon j within clinic k . The variables t_1 ($=1, 2, 3, 4, 5, 6, 7$) and t_1^2 ($=1, 4, 9, 16, 25, 36, 49$) are the linear and quadratic terms for wave with the corresponding coefficients β_1 and β_2 representing the fixed linear and quadratic effects to model the underlying secular trend. The variable z ($=0, 1$) denotes if patient i was enrolled during the post-COVID restart time period for a given clinic with the corresponding fixed effect coefficient β_3 . The variable t_2 ($=0, 1, 2, 3, 4, 5, 6$) denotes if patient i was enrolled within the first wave post-COVID restart time period ($t_2 = 1$); within the second wave post-COVID restart time period ($t_2 = 2$); and so on through the sixth wave post-COVID restart time period ($t_2 = 6$). The maximum value is $t_2 = 6$ because when the stepped-wedge design was suspended all clinics were at least enrolling part way in wave 2 of the possible 7 waves. For patients enrolled prior to the post-COVID restart time period the value of $t_2 = 0$. The random effect u_k is the level-3 (clinic) random intercept effect (random clinic variance); the random effect $u_{j(k)}$ is the level-2 random intercept effect for

the $j(k)^{th}$ level-2 unit (random surgeon variance nested in clinics); the random effect $e_{i(j(k))}$ is the random individual variance within surgeons nested in clinics. The term β_0 is the intercept. The term θ represents the intervention effect of the decision aid and is the primary effect of interest.

Models will adjust for the a priori specified patient characteristics described above that are likely to be strongly predictive of the endpoints. In the event that the approximately continuous outcomes PEPPi-5 self-efficacy and Active Patient Participation Behaviors are not approximately symmetrically distributed, variable transformation will be considered (e.g., square-root transformation). Further, as part of the planned efficacy analysis we will fully test the variance-covariance structure of the model, while blinded to any treatment effects, which may lead to a more parsimonious model.

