We will first perform analyses to test and quantify the extent to which the effect of the decision aid intervention on patient engagement endpoints is mediated through the mitigation of candidate preparatory and interactional barriers. We will quantify the indirect effect relative to the total effect of the decision aid in joint linear structural equation models (SEM) for the endpoint and the candidate mediators, including random surgeon effects and random region effects for each of the mediator and endpoint parts of the models. Each of the preparatory and interactional Barriers will be represented by a continuous latent construct in the SEM, with 3 and 5 observed items for Preparatory and Interactional Barriers, respectively. Binary or count variables will be modeled via latent continuous construct in the SEM. Structural equation models will be specified, estimated and tested using Mplus v7.3.⁹⁷ The use of unidimensional latent constructs increases power and reduces the number of tests, relative to testing each observed item separately. Standardized coefficient estimates from the SEM, representing total, direct, and indirect effects, will allow for the determination of whether the mechanism by which the decision aid leads to increased patient engagement is through the mitigation of preparatory and/or interactional barriers (see Figure 7 for simplified example). For example, if coefficient X is important but Y is not, we can conclude that although the decision aid leads to statistically significant changes in interactional barriers, this is not the mechanism through which the decision aid increases patient engagement. Alternatively, if only coefficient Y is important, we can conclude that although the interactional factors represent a significant barrier to patient engagement, the decision aid does not significantly impact the barrier.

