Finally, if we find significant indirect effects (represented in the figure by the dashed line leading from the decision aid to engagement that runs through interactional barriers), we can conclude that receipt of the decision aid leads to a change in the interactional barrier, which leads to improved patient engagement. Statistically, coefficients X and Y will be tested together, with the null hypothesis being that the product $XY=0$. If either latent construct for preparatory or interactional Barriers is significant, then each individual observed item will be tested, post hoc, as candidate barriers. Candidate barriers for the next models will be barriers for which the indirect effect is significant and/or barriers associated with lower levels of engagement (i.e. coefficient Y). Those barriers associated with lower level of engagement will be considered persistent and prioritized for inclusion in the qualitative interviews (Aim 3).

Persistent Barriers Experienced by Socioeconomically Disadvantaged Patients

We will estimate logistic and Poisson regression models with socioeconomic deprivation as the explanatory variable, and each candidate persistent barrier as described above as the outcomes, in order to assess the extent to which socioeconomic disadvantage is associated with persistent barriers to engagement. As with Aim 1, models will include surgeon and clinic random effects to account for patient clustering. Findings will guide the sampling strategy for patient interviews (Aim 3) and will be incorporated into the interview content.

[figure not shown]

Figure 7. Schematic depicting the mediating role of preparatory and interactional barriers on engagement. The dashed lines represent the test for the overall effect of whether the decision aid improves engagement through that pathway.

*Effect of decision aid on barriers; +Effect of barriers on patient engagement.

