Co-Primary Objective #2: Mackinnon *et al.* have shown that one of the most accurate tests for mediation or indirect effect is the “asymmetric distribution of products” test¹⁰⁰ and have provided extensive simulation studies for estimating power for a variety of mediation tests.^{101,102} PowMedR software¹⁰³ was developed based on that work, which we exploit here. We assume a sample size of 563 and then deduct 23 df for surgeon effects and 7 df for number of waves; we estimate an effective sample size of 533. In addition, because we are testing two mediators, we set $\alpha=0.05/2 = 0.025$ for these two tests. Suppose we have small mediation effects with $R^2=2\%$ for the effect of the intervention on the *latent* barrier mediator (Figure 7) and for the effect of the latent mediator on PEPPi-5 score or on active patient participation behavior count. Suppose additionally that the three observed items have correlation of at least $r=0.60$. Then, the average of those three items will have reliability of $\lambda = \{r + (1/3)(1 - r)\}$, yielding net R^2 values between the intervention and the *observed* mediator and between the observed mediator and PEPPi-5 score or active patient participation behavior count of $\lambda R^2=0.82*.02=1.6\%$. Using the PowMedR software, we will have 60% power to detect mediation with small effect size and >99% power to detect mediation with medium effect size $\lambda R^2=0.82*.15=12.3\%$. Power will be higher with five items.

We will extend the period of enrollment for sites that are still recruiting within the stepped wedge design as of 8/30/2021. The extended recruitment beyond Wave 7 will continue for six sites until 12/31/2021 (see Section 12.1.3). While these additional patients will not contribute to the first co-primary objective, they will be included in the analysis for this 2nd co-primary objective; all of these additional patients will be exposed to the study intervention. We anticipate, at a minimum, that there will be 50 such patients exposed to the intervention across these six sites. We re-estimated power assuming such an increase, which leads to an increase in the power for detecting small effects from 60% to 65%.

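### The mediation model for Co-Primary Objective #2 names no patient covariates, so if the aid shifts a barrier, a shared patient trait can make XY significant with no barrier effect; the planned causal reading is not supported

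*Combined protocol and SAP*

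**What the plan says.** Section 12.1.1 (Co-Primary Objective #2) plans a joint linear structural equation model for the engagement endpoint and the latent preparatory and interactional barriers, "including random surgeon effects and random region effects for each of the mediator and endpoint parts of the models". No patient-level covariate is named. X is the effect of the aid on the barrier and Y the effect of the barrier on engagement. The null is XY = 0, and on rejection "we can conclude that receipt of the decision aid leads to a change in the interactional barrier, which leads to improved patient engagement".

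The same section sends a barrier on to the later models if its indirect effect is significant and/or if it is associated with lower engagement, that is, on Y alone. Barriers of the second kind are called persistent and are prioritised for interviews.

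The only sentence on covariates stands in the text for Co-Primary Objective #1: "Models will adjust for the a priori specified patient characteristics described above that are likely to be strongly predictive of the endpoints". Nothing extends it to the structural equation model. For the later deprivation models the plan refers back to Aim 1, but only to carry over the surgeon and clinic random effects.

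For the mediation tests, section 12.1.2 says "we set $\alpha=0.05/2 = 0.025$ for these two tests" and "we estimate an effective sample size of 533".

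**The concern.** Clinics are randomised to crossover time, so X has a randomised basis. Y does not: it is an observational association between the barrier and engagement. A patient characteristic that affects both will bias Y, and adding time terms does not remove this.

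The protocol itself supplies a candidate. Section 1.1 reports that disadvantaged women understand treatment options less well and take part less actively in decisions, and section 1.2 says the barriers may fall disproportionately on them. On that premise disadvantage raises the barrier and lowers engagement. This is the direction that would make a fall in the barrier look like the route to better engagement. The Area Deprivation Index is collected but enters only in a later, separate model.

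At stake is the mechanism claim of a co-primary objective, and the list of barriers taken into the interviews.

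**Working it through.** **Inputs from section 12.1.2.** Effective n = 533. Alpha is 0.025 per mediator (two-sided assumed; critical z = 2.241). Small path R² = 0.82 × 0.02 = 0.0164 on the observed mediator.

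**Reproducing the stated power.** For one path, z = √[R²/(1−R²)] × √(n−2).
- n = 533: √(0.0164/0.9836) × √531 = 2.975. Power per path is Φ(2.975 − 2.241) = 0.769, and for both paths 0.769² = 59%. The plan states 60%.
- n = 583: z = 3.112, path power 0.808, both paths 65%. The plan states 65%.

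A Monte Carlo distribution-of-products test gives 57% and 64%. The joint test is therefore a fair stand-in. (The printed reliability formula gives 0.60 + 0.40/3 = 0.733. The 0.82 is 3r/(1+2r) = 1.8/2.2, and the stated power follows from 0.82.)

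**False mediation with no barrier effect (true Y = 0).** Assume one trait correlates t with the barrier and with the endpoint, given aid status. It induces a barrier–endpoint correlation r = t². Then z_Y = r/√(1−r²) × √530, and the product is declared significant with probability P(X significant) × P(Y significant).

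- X R² = 1.64%: P(X) = 0.769, as above.
- X R² = 2%: z = √(0.02/0.98) × √531 = 3.292, P(X) = 0.853.
- X = 0: P(X) = 0.025.

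| t (assumed) | r | z_Y | Y alone | XY, X = 0 | XY, X R² 1.64% | XY, X R² 2% |
|---|---|---|---|---|---|---|
| 0.2 | 0.04 | 0.92 | 9% | 0.2% | 7% | 8% |
| 0.3 | 0.09 | 2.08 | 44% | 1.1% | 34% | 37% |
| 0.4 | 0.16 | 3.73 | 93% | 2.3% | 72% | 80% |

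Simulated regressions with 533 independent patients agree: 7–8%, 31–38% and 70–79% for the product with small X, and about 8–9%, 43% and 93% for Y alone with X = 0.

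**Allowing for the design.** Treating 533 patients as independent and evenly split gives X a standard error of 2/√533 = 0.087 SD. The Objective #1 detectable effects (0.50 and 0.55 SD at 80% power) imply 0.50/(2.241+0.842) = 0.162 and 0.55/3.083 = 0.178, or about 0.17 SD. With X R² = 2% the shift is 2√(0.02/0.98) = 0.286 SD, so z = 0.286/0.17 = 1.68 and P(X) = 0.288. The product is then falsely significant in 0.288 × (0.094, 0.436, 0.932) = 2.7%, 12.5% and 26.8% of trials. With X R² = 1.64% (0.258 SD, P(X) = 0.235) the figures are 2%, 10% and 22%.

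**After adjustment.** With the trait in both equations, simulated false mediation is about 2–3% at either X size, and well under 1% when X = 0. If the trait is measured with reliability 0.7, adjustment leaves about 5% at t = 0.3 and 13–14% at t = 0.4 (small X, independent patients).

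**The case against.** **The test does not reject whenever a trait drives both variables.** A reader might infer that it does. A shared trait biases only Y; if the aid leaves the barrier unchanged, the product test stays at or below about 2.5%. At t = 0.2 with a stepped-wedge standard error it is about 3%, close to nominal. This objection stands.

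**The larger rates use a favourable standard error.** This also stands. They match the plan's own power inputs, but not the precision the design gives for X, so both sets are shown.

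**Silence is not exclusion.** The structural equation text does not list every term: it omits wave, although section 12.1.2 deducts 7 degrees of freedom for waves. The documents support saying that no patient covariate is named, not that none will be used. But the one adjustment sentence belongs to Objective #1, and a causal conclusion needs its covariates stated.

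**Patient traits may matter less for interactional barriers.** The sentence quoted on causation concerns these. By section 10.1.4.2 several of their measures come from the surgeon's baseline survey or the audio recording, and a patient trait cannot drive the surgeon's questionnaire. Large correlations are less plausible there than for preparatory barriers. This limits the size, not the logic.

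**Health literacy is not a clean baseline covariate.** Section 10.1.4.3 places it among accessibility barriers: "We use the Brief Health Literacy Screen (BHLS) to evaluate health literacy in clinical practice". It looks like an obvious adjuster, but after crossover the T0 survey is answered after the aid has been sent, and one item asks about difficulty learning about one's condition, which the aid could change.

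**Conclusion.** The point holds in conditional form. If the aid shifts a barrier, an unadjusted trait that drives both barrier and engagement can make XY significant although the barrier does nothing, and the plan would report a causal chain. For trait correlations of 0.2 / 0.3 / 0.4 the size is about 7–8% / 31–38% / 70–79% on the plan's small-effect inputs, or about 3% / 13% / 27% with a standard error of 0.17 SD for X, against 2.5%. The correlations are assumptions; the documents give none. The calculations also assume two-sided tests, a single trait and no clustering in Y.

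Selection on Y alone is more exposed, because it needs no effect of the aid: Y is falsely significant in about 8–9% / 43–44% / 93% of trials.

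A reader might also infer that the product test settles which barriers become intervention targets. The documents do not say that: candidates can enter on Y, and section 12.2.1 ranks targets after integrating the interviews, by how common each barrier is and its perceived impact.

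**What to change.** In section 12.1.1, Co-Primary Objective #2:

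1. Enter the same pre-exposure covariates in both the mediator and the endpoint equations: age, race/ethnicity, payer, ADI category and clinical stage. All are already collected.
2. Add the T0 Brief Health Literacy Screen only as a sensitivity analysis, because it may be a post-exposure measure in the intervention period.
3. Prespecify a sensitivity analysis that reports the residual mediator–endpoint correlation at which each significant indirect effect loses significance.
4. Replace the causal sentence with one saying that the data are consistent with mediation, assuming no remaining mediator–endpoint confounding. Attach the same caveat to barriers selected on Y alone.

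The cost is SAP wording, a few model terms and a few degrees of freedom. The indirect effect may be smaller and less often significant where part of Y was confounding. Covariates remove only the confounding they measure, which is why item 3 is needed as well as item 1.

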1.3 Gap Addressed in this Study

Our study is founded on the scientific premise that breast cancer surgery decision aids improve knowledge for most patients (necessary but insufficient alone to ensure engagement in SDM).^{2,4-6,35,36} Based on our conceptual model, we posit that receipt of a decision aid prior to the surgical consult will also empower some patients, resulting in increased engagement in SDM. However, other patients will experience persistent preparatory or interactional barriers that cannot be addressed by the decision aid alone.

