We use an explanatory mixed methods approach to integrate the quantitative (primary objectives) and qualitative (secondary objective) findings in order to identify potential targets for adjunct interventions.⁹¹ The quantitative analysis will identify and prioritize persistent barriers to engagement that exist with and without a decision aid. By understanding patients' experiences with these barriers, we can obtain insight into potential ways to ameliorate them. From this integration, we will identify a list of potential targets for adjunct interventions, prioritized by the proportion of patients who experience the barrier and perceived impact of the barrier on engagement.

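### Item-level barrier testing appears to depend on significant mediation, so a barrier that the decision aid leaves unchanged would rarely reach it

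*Combined protocol and SAP*

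**What the plan says.** Section 12.1.1 (Co-Primary Objective #2) represents preparatory and interactional barriers by one latent construct each, with three and five observed items. X is the effect of the decision aid on the barrier; Y is the effect of the barrier on engagement.

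- Formal test: "coefficients X and Y will be tested together, with the null hypothesis being that the product" XY is zero.
- Condition for looking at items, in the next sentence: "If either latent construct for preparatory or interactional Barriers is significant, then each individual observed item will be tested, post hoc, as candidate barriers". It does not say on which coefficient the construct must be significant.
- Selection for the next models: "Candidate barriers for the next models will be barriers for which the indirect effect is significant and/or barriers associated with lower levels of engagement", with Y named as the coefficient for the second route.
- Definition of persistence: "Those barriers associated with lower level of engagement will be considered persistent and prioritized for inclusion in the qualitative interviews".
- Slightly earlier, the case of a barrier that the aid does not change is foreseen: "if only coefficient Y is important, we can conclude that although the interactional factors represent a significant barrier to patient engagement".

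Section 12.1.2 gives a significance level (0.05/2 = 0.025, for two mediators) and power only for the mediation test. It then starts the disadvantage models once mediating barriers have been found, budgeting up to four barriers at 0.05/4 = 0.0125 each. Section 12.2.1 gives the purpose of this step: "The quantitative analysis will identify and prioritize persistent barriers to engagement that exist with and without a decision aid". Section 1.3 expects that "other patients will experience persistent preparatory or interactional barriers that cannot be addressed by the decision aid alone".

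**The concern.** A barrier can matter greatly for engagement and still be untouched by the aid. It then has a large Y but X = 0, so XY = 0. If the condition for item testing is a significant XY, it will nearly always fail for such barriers, although they fit the plan's own definition of persistence.

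The second half of Co-Primary Objective #2 asks whether disadvantaged patients experience persistent barriers disproportionately. Its models are logistic and Poisson regressions with each candidate barrier as the outcome. A continuous latent construct is not an outcome of that kind, so these models need barriers identified at item level. If no item is tested, that half of the objective and the prioritised list of persistent barriers have nothing to work on. Two analysts following the text could also reach opposite decisions about whether to run the analysis at all.

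**Working it through.** **Inputs (Section 12.1.2).** Effective sample size 563 − 23 − 7 = 533, or 583 with the 50 patients added after Wave 7. Alpha is 0.025 per construct, taken as two-sided (critical value 2.241). The small effect per path is R² = 0.82 × 0.02 = 0.0164.

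**1. Reproducing the plan's power.** Treat mediation as both paths being significant.
- Noncentrality per path = √(n·R²/(1 − R²)). At n = 533: √(533 × 0.0164/0.9836) = 2.98.
- Power per path = Φ(2.98 − 2.241) = 0.770.
- Both paths: 0.770² = 59.3%. At n = 583: 0.810² = 65.5%.

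The plan states 60% and 65%, so its figures are reproduced. A distribution-of-product test, the type that the plan cites, gave 56.9% and 64.1% by simulation.

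**2. The aid leaves both constructs unchanged (X = 0), and XY is the condition.** X is then significant with probability 0.025.

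| Y path (R²) | P(Y significant) | XY significant, one construct | Either of two constructs |
|---|---|---|---|
| 0.0164 (plan's small effect) | 0.770 | 0.025 × 0.770 = 0.0193 | 1 − (1 − 0.0193)² = 3.8% |
| 0.05 (assumed) | 0.999 | 0.025 | 4.9% |
| 0.123 (plan's medium effect) | 1.000 | 0.025 | 1 − 0.975² = 4.9% |

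The simulated product test gives 1.6% per construct for the small Y path, or 1 − (1 − 0.016)² = 3.2% for either. If a significant result on either of the two endpoints counted, the ceiling would be 1 − 0.975⁴ = 9.6%. All of these assume independent tests.

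**3. A construct may qualify on Y alone.** One construct with the small Y path is detected with probability 77.0% at n = 533 and 81.0% at n = 583. With R² of 0.05 or more it is 99.9% or higher.

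**4. One construct is mediated, the other unchanged.** With the plan's 60% power for the first, item testing opens in 1 − 0.40 × 0.975 = 61% of trials. The low figures in step 2 therefore belong to the case where the aid moves neither construct.

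**5. Which reading the text favours.** Three things point to XY: the condition follows directly on the XY null; only the mediation test has an alpha and a power figure; and Section 12.1.2 makes mediating barriers the starting point of the disadvantage models. Three things point to Y: the and/or selection rule, the definition of persistence, and the purpose stated in Section 12.2.1.

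**The case against.** The condition in Section 12.1.1 does not contain the word mediated, and the same section interprets X and Y separately. It foresees a barrier that only Y supports and states a conclusion for it. The selection rule then offers a route through Y. On a generous reading the authors meant significance on either coefficient, and nothing is lost. That reading is possible, but the Y-only case has no test or alpha at construct level, no stated step leads from it to the items, and Section 12.1.2 speaks of mediating barriers. The objection turns a certain failure into a conflict between passages; it does not remove the conflict.

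A reader might infer that no persistent barrier could be identified at all and that the interviews would have no input. The documents do not support this. Section 8.3.2 samples interviewees on low engagement and experienced barriers without any significance test, accessibility barriers are handled descriptively, and Section 12.2.1 adds inductive coding for unmeasured barriers. A construct-level conclusion on Y also remains available.

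It is also fair that X need not be exactly zero. Section 1.3 expects the aid to empower some patients and not others, which is a partial effect. One significant construct is enough to open item testing, and the plan states power above 99% for a medium mediated effect. Finally, testing constructs first has a stated rationale: more power and fewer tests.

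**Conclusion.** The point holds as a conflict within the plan. On its natural reading, the condition for item testing is a mediation test, whereas the barriers sought are defined by Y. If the aid changes neither construct, item testing opens in about 3.8% of trials with the plan's small Y path and in at most 4.9% with a strong one. Qualifying on Y would detect one such construct about 77% of the time. These figures assume X exactly zero in both constructs, one endpoint, independent tests, and the plan's effective sample size and R².

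The loss would be the item-level list of persistent barriers and the disadvantage half of Co-Primary Objective #2. It does not extend to the interviews or to construct-level conclusions. Choosing between the readings after seeing the results would be a data-driven decision, so the wording should be settled before the analysis.

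**What to change.** 1. In Section 12.1.1, state that each observed item is tested for association with engagement (Y) whatever the XY result, with Holm adjustment across the items. A weaker alternative, which keeps the construct-first approach, is to test items whenever the construct's Y path is significant, with an alpha stated for that test.
2. In Section 12.1.2, replace mediating barriers as the starting point of the disadvantage models by candidate persistent barriers as Section 12.1.1 defines them.
3. Keep the XY test only for the claim that the aid works through a barrier.

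**Cost.** This is a change of wording, with up to eight item tests (3 + 5) sharing one error rate. More than the four budgeted barriers might go forward to the disadvantage models. With eight, alpha per test would be 0.05/8 = 0.00625. The effect detectable with 80% power would rise by the factor (2.734 + 0.842)/(2.498 + 0.842) = 1.07, from 0.31 to about 0.33. The plan should either accept that or state how the number going forward is limited to four.
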